The anticipated outcome is decreased in-hospital opioid consumption for those patients treated with intravenous lidocaine. Other anticipated outcomes are improved recovery as measured by PROMIS-M and PROMIS-PI measures at 6 weeks, 3 months, 6 months, and 12 months after surgery. We anticipate that the anti-inflammatory effect of lidocaine will reflect a smaller postoperative inflammatory response as measured by IL-10, IL-4, and IL-12.

F3 Safety and Adverse Events

Serum lidocaine levels will be drawn at 12 hours after incision and reviewed by an individual independent from the study team. Lidocaine toxicity will result in immediate cessation of study drug, unblinding, and reporting to the Medical Monitor and IRB. If intraoperative surgical, medical, or anesthetic complications occur, including cardiac arrhythmia, the study medication will be stopped and the patient withdrawn from the study. The patient will be analyzed in an intent-to-treat analysis, though they will be excluded from as-treated analyses. After surgery, patients will be seen and examined twice daily with attention to postoperative complications. As the study-drug will have completed infusion, all complications will be recorded though patients will remain enrolled in the study and analyzed per-protocol. All adverse events will be recorded up to 12 weeks after surgery. These will be captured via interview at the visit or via telephone if a clinic visit is not possible. Readmission for any reason will be recorded and details of this hospitalization will be recorded. Any reason reasonably related to the research protocol will be reported to the Medical Monitor and the IRB.

We believe there are minimal risks associated with participation in this clinical trial and with the study intervention (intravenous lidocaine). The most concerning serious adverse event that might be attributed to systemic lidocaine administration is cardiac arrhythmia/arrest. Therapeutic serum concentrations are far lower than toxic levels and we believe the risk of serious adverse events to be low. The intervention will not add time to the surgical intervention and, thus, does not pose additional risk from this perspective. All patients will receive standard of care treatment before, during, and after surgery and the study intervention will pose no risk to this.

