Safety measures to minimize/eliminate risks to human subjects and study personnel include the use of the Medical Monitor and immediate reporting of any adverse (expected or unexpected) to the project PI and project manager. If any intraoperative complications occur, such as but not limited to cardiac arrest or seizure, the study medication will not be administered and the patient will be excluded from the study. However, if one of these problems occurs after the application of the study medication the patient will be unblinded. The patient will be followed for the occurrence of further adverse events or complications.

For any serious adverse event, the Medical Monitor at the enrollment site will perform a root cause analysis and will notify the project PI in the study medication is believed to be a potential cause of the adverse event. The Monitor may recommend stopping the study. Any serious adverse event will be reported to the PI and the IRB within 10 working days.

F4 Study Outcome Measurements and Ascertainment

The primary outcome measure is total, in-hospital opioid consumption following surgery for thoracolumbar trauma. Opioid consumption will be measured in morphine-equivalent dosage (MED), to allow for the use of different opioid medications (e.g. fentanyl, hydromorphone, oxycodone) over the course of care.

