Secondary outcome measures to assess recovery are the Patient Reported Outcomes Measurement Information System (PROMIS) Mobility (M) and Pain Interference (PI) domains. PROMIS is a general measure of health administered over particular health domains. This instrument has been tested extensively and is reliable and precise.⁴⁵ Scores range from 0-100 and are normalized so that a score of 50 is the population mean, with 10 points representing a standard deviation is 10 points. For the Mobility domain larger scores represent more function; for the PI domain larger scores represent more pain. The instrument administered via computer-adaptive testing (CAT) to minimize question burden. The Scoliosis Research Society 22 (SRS-22) will be used in assessing the quality of life in AIS patients. The SRS-22r includes 22 items distributed among five different factors (pain, self-image/appearance, function/activity, mental health, and satisfaction with management). Each component includes five items, except for the “satisfaction with management”, which only contains two items. Secondary measures to assess the anti-inflammatory effect of lidocaine will be serum levels of IL-10, IL-4 and IL-12.

The anticipated outcome is decreased in-hospital opioid consumption for those patients treated with intravenous lidocaine. Other anticipated outcomes are decreased opioid consumption at three-months after surgery, with improved recovery as measured by PROMIS-M and PROMIS-PI measures at 6 weeks, 3 months, 6 months, and 12 months after surgery. We anticipate that the anti-inflammatory effect of lidocaine will reflect a smaller postoperative inflammatory response as measured by IL-10, IL-4, and IL-12.

G Statistical Plan

G1 Sample Size Determination and Power

The target sample size of 50 patients, 25 per group, is based upon a two-tail test at the 0.05 level of significance, with 80% power to detect an effect size of $d=0.8$. Prior data from our institution has shown an average postoperative morphine-equivalent consumption of 149 mg with a standard deviation of 37 mg. The proposed effect size is equivalent to approximately a 20% reduction in postoperative morphine-equivalent opioid consumption. The primary outcome measure is the inpatient measure of postoperative opioid consumption. As such, loss-to-followup is not possible, though 25 per group accounts for 10% loss due to treatment noncompliance which is unlikely.

G2 Analysis Plan

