After the first 15 patients are enrolled, a group consisting of the Principal Investigator and an unengaged physician will review the AE/SAE data. The data will be reviewed blinded. If intraoperative surgical, medical, or anesthetic complications occur, including cardiac arrhythmia, the study medication will be stopped and the patient withdrawn from the study. The patient will be analyzed in an intent-to-treat analysis, though they will be excluded from as-treated analyses. After surgery, patients will be seen and examined twice daily with attention to postoperative complications. As the study-drug will have completed infusion, all complications will be recorded though patients will remain enrolled in the study and analyzed per-protocol.

Special attention will be given if adverse events occur in a higher frequency than expected given patient age and health condition. Serious adverse events, or those that are life threatening, result in death, prolonged hospitalization, readmission, cause persistent disability or require urgent intervention to prevent permanent morbidity will be monitored for up to 30 days after the drug is administered. If there appears to be an imbalance in AE/SAE, unblinding and analysis will ensue to determine if the study should continue. Early termination will occur if SAEs are linked to the treatment arm.

After 10 patients have completed the hospital phase of the study, flow and mass cytometry will be performed to ensure we are capturing cell types and signaling proteins as anticipated.

All protocol violations and SAE's will be reported to HRPO within the WU HRPO policies and procedures reporting guidelines
SAEs will be tracked through resolution.

J References

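### Stopping study drug for an intraoperative complication is tied to an undefined withdrawal from the study, and no text secures the outcomes that the promised intent-to-treat analysis needs

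*Combined protocol and SAP*

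**What the plan says.** F3 (Safety and Adverse Events) and I1 (Study Monitoring Plan) carry the same rule. If a surgical, medical or anesthetic complication occurs during the operation, "the study medication will be stopped and the patient withdrawn from the study. The patient will be analyzed in an intent-to-treat analysis". Both then leave the patient out of the as-treated analyses. For complications after surgery, both say that "all complications will be recorded though patients will remain enrolled in the study and analyzed per-protocol".

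A later paragraph of F3 covers overlapping events, naming cardiac arrest and seizure as examples, and gives a different rule. If the drug has not yet been given, "the study medication will not be administered and the patient will be excluded from the study". Otherwise, "if one of these problems occurs after the application of the study medication the patient will be unblinded". It then adds: "The patient will be followed for the occurrence of further adverse events or complications". This second rule does not mention withdrawal, intent-to-treat or the efficacy outcomes.

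G1 says of the primary outcome: "As such, loss-to-followup is not possible". The same sentence adds a 10% allowance for treatment noncompliance. G2 describes inspecting missing-data patterns and comparing completers with dropouts. It does not define the intent-to-treat set or name a method for missing outcomes.

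**The concern.** Stopping a drug and leaving a study are different events, and only the first is needed for safety. An intent-to-treat analysis needs outcomes after the drug is stopped. Here one sentence joins the two events and the next promises the analysis, with nothing in between to say that collection goes on.

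The timing matters. The event happens in the operating room, before postoperative MED has accrued, before the day 1 and day 2-3 bloods, and before every postoperative PROMIS and SRS-22 assessment. Two coordinators could follow this text in good faith and produce different datasets. One would keep abstracting, sampling and contacting the family. The other would record adverse events only.

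Any resulting gaps would not be random. They would be confined to patients with complications, whose opioid use and recovery may well be atypical, and they could differ by arm. The intent-to-treat comparison would then in effect be a complete-case comparison of patients without an intraoperative complication. The bloods serve Specific Aim 2, which the protocol lists among its primary aims.

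**Working it through.** **Reading the rules side by side.**

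| Event | Place | Status in study | Collection stated afterwards |
|---|---|---|---|
| Intraoperative complication | F3, first rule; I1 | withdrawn; kept for intent-to-treat, out of as-treated | none stated |
| Intraoperative, before drug | F3, second rule | excluded | none stated for efficacy |
| Intraoperative, after drug | F3, second rule | unblinded | adverse events and complications |
| Postoperative complication | F3; I1 | remains enrolled | complications recorded |

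The contrast between the first and last rows makes the natural meaning of withdrawn no longer enrolled. The bolus is given at induction (E1, E3 3.b, F2), so most intraoperative events would come after drug has started. Both the first rule and the third row would then apply to the same patient.

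**Which outcomes are exposed.**
- MED: H1 says the primary data come from the medical record, so MED is recoverable if abstraction continues. The plan does not say that it does.
- Research bloods (F2: 4 and 8 hours post incision, day 1, day 2-3): any not yet drawn are lost for good.
- PROMIS and SRS-22 (C2: 6 weeks, 3, 6 and 12 months): these need continued contact and cannot be rebuilt from a chart.

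**The plan's own figures.** G1 gives d = 0.8, SD 37 mg, mean 149 mg, two-sided 0.05 and 80% power.
- Design effect: 0.8 × 37 = 29.6 mg, and 29.6 / 149 = 19.9%, matching the stated 20% or so.
- Sample size by the normal approximation: 25 per group, as stated. The t-test gives 25.5, so 26. The 25 is therefore the number needed with no loss.

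**Illustrative size (rates and excesses are assumptions).** At an overall rate of 5% to 15%, 50 × 0.05 = 2.5 to 50 × 0.15 = 7.5 patients would be affected.

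If MED is also lost, and affected patients use e mg more than others in their arm, dropping them lowers each arm's mean by rate × e. The difference moves by (rate in lidocaine − rate in placebo) × e. With e = 1 SD = 37 mg:
- 12% against 4%: 0.08 × 37 = 2.96 mg, and 2.96 / 29.6 = 10% of the design effect.
- 20% against 4%: 0.16 × 37 = 5.92 mg, and 5.92 / 29.6 = 20%.

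With losses in one arm only, 1 to 3 of 25 patients and an excess of 0.5 to 2 SD give 1 × 0.5 × 37 / 25 = 0.7 mg up to 3 × 2 × 37 / 25 = 8.9 mg.

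For scale, the standard error of the difference is 37 × √(2/25) = 10.5 mg, so 2.96 and 5.92 mg are 0.28 and 0.57 of it.

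**Power if MED is lost (t-test, d = 0.8).** 79.1% at 25 per group; 77.4%, 75.6% and 73.6% with 1, 2 or 3 lost per group.

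**PROMIS on the same assumptions.** F4 gives a population SD of 10. A 1 SD worse score among affected patients shifts the difference by 0.08 × 10 = 0.8 or 0.16 × 10 = 1.6 points. The plan sets no target difference for PROMIS against which to judge this.

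**The case against.** The strongest reply is that a promise of intent-to-treat analysis only makes sense if outcomes are kept, so the authors probably meant withdrawal from treatment. E2 2.c supports this: in-hospital outcomes will be collected during the stay, and all efforts will be made to obtain follow-up. MED sits in the chart in any case. This reading is plausible. It stands as a reason not to assume that data will be lost, above all for the primary outcome. It does not settle the matter, because neither 2.c nor any other section addresses patients who have been withdrawn.

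Three stronger readings are tempting, and the documents do not support them:
- A reader might infer that the protocol orders outcome collection to end. No section says so; it is silent.
- A reader might infer that the protocol expects more arrhythmia on lidocaine, so that loss must differ by arm. F3 calls arrhythmia or arrest the most concerning serious event that might be attributed to the drug, and considers the risk low. Differential loss is possible but not predicted.
- A reader might infer that the primary result is badly compromised. Even if MED were lost, the illustrated 3.0 and 5.9 mg shifts are about a quarter to just over half of one standard error.

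It is also fair to note G1's 10% allowance. That allowance is for noncompliance rather than missing outcomes, and 25 per group leaves no room for it.

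**Conclusion.** The point holds as a conflict of wording with consequences for data. F3 and I1 join stopping study drug to an undefined withdrawal while promising intent-to-treat analysis of the same patients. F3's second rule treats overlapping events differently, and nothing beyond adverse-event follow-up is secured.

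The exposure is greatest for the remaining bloods and the PROMIS and SRS-22 assessments, which are irrecoverable once missed. It is weaker for MED, where the gap is whether abstraction continues.

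The size cannot be taken from the documents. The MED shifts of 3.0 and 5.9 mg against 29.6 mg rest on assumed complication rates, an assumed 1 SD excess and the further assumption that MED is not abstracted. The direction also depends on which arm has more complications and whether those patients use more opioid. What is certain is that the plan allows the loss, and that G1's statement that it cannot occur does not account for withdrawals the protocol itself requires.

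**What to change.** - In F3 and I1, separate discontinuation of study drug from withdrawal from the study. State that MED, the scheduled bloods, PROMIS and SRS-22 to 12 months, and adverse events continue to be collected for every randomised patient unless consent is withdrawn.
- Record the time and reason of drug stop in a field separate from study withdrawal.
- Reconcile F3's second rule (exclusion before drug; unblinding and follow-up after drug) with the first rule and with I1, so that every randomised patient stays in the intent-to-treat set. Extend its follow-up sentence to the efficacy outcomes.
- In G2, define that set as all randomised patients and say how outcomes that are still missing will be handled.
- Qualify G1's statement on loss to follow-up.

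Nothing here changes when or why drug is stopped. The cost is a wording amendment and one or two case report form fields. MED is already in the record, and the samples, visits and contacts are already planned for every patient.

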The low plasma levels have not been associated with hemodynamic instability nor have they been associated with changes in cardiac contractility. No interactions with the autonomic nervous system have been reported and there are no known effects on sinoatrial conduction. Lidocaine is metabolized by the liver, with less than 10% excreted in urine. Complications are rare. Despite concerns for arrhythmias, intravenous lidocaine has been used in cardiothoracic surgery without increased rates of cardiac complications. Given this volume of evidence, we feel that intravenous lidocaine in the setting of AIS surgery is safe.

3.b Treatment Regimen

After a 1mg/kg IBW lidocaine bolus with induction, a lidocaine 1 mg/kg/hr (IBW) IV infusion with maximum dose of 200 mg/hr or D5W (placebo) at equal volume rate of administration will begin prior to skin incision and continue intraoperatively for duration of the case. Study drug will be discontinued upon 24 hours of stay in either PACU or PICU postoperatively.

Method for Assigning Subjects to Treatment Groups

Patients consenting to randomization will be randomized 1:1 to the control vs study groups. A permuted randomized block approach¹ with blocks of size 4, 6 and 8. Given the relatively large number of patients to be enrolled, no stratification will be performed. After 30 patients are enrolled, an interim analysis, without unblinding, of baseline covariates will be performed to ensure equal distribution between groups. If distribution is uneven for covariates concerning for confounding, then stratification by these covariates will be employed to ensure equal distribution with randomization.

3.c Blinding of Study Drug

This is a Phase IV, randomized, triple-blind, placebo-controlled trial with two study groups: postoperative standard of care with opioid patient controlled analgesia (PCA) and IV lidocaine infusion versus postoperative standard of care plus normal saline placebo. Block randomization into one of the two groups will be based on a random table generated using an R-program. Group 1 (Study) will receive intravenous lidocaine during and after posterior spinal fusion for AIS. Group 2 (Control) will receive saline placebo during and after surgery.

F Study Procedures

F1 Screening for Eligibility

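### The as-treated analysis drops patients whose study drug was stopped for an intraoperative complication, although they have normally been exposed to it

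*Combined protocol and SAP*

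**What the plan says.** The rule appears in the same words in F3 (Safety and Adverse Events) and I1 (Study Monitoring Plan). The trigger is: "If intraoperative surgical, medical, or anesthetic complications occur, including cardiac arrhythmia, the study medication will be stopped and the patient withdrawn from the study". The analysis consequence follows: such patients are kept in the ITT analysis, "though they will be excluded from as-treated analyses". It covers both arms and any intraoperative complication.

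For complications after surgery, both sections say that "all complications will be recorded though patients will remain enrolled in the study and analyzed per-protocol". The reason given is that the infusion is over by then.

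On exposure, 3.b (Treatment Regimen) and F2 give a bolus with induction and an infusion that "will begin prior to skin incision and continue intraoperatively for duration of the case". Both, like E1, run study drug until 24 hours of PACU or PICU stay.

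F3 also says: "The most concerning serious adverse event that might be attributed to systemic lidocaine administration is cardiac arrhythmia/arrest".

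A later paragraph of F3 handles intraoperative complications differently: "the study medication will not be administered and the patient will be excluded from the study". It adds that "if one of these problems occurs after the application of the study medication the patient will be unblinded", with follow-up for further events.

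The plan does not define the as-treated set or say which outcomes use it, and G2 (Analysis Plan) does not mention it.

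**The concern.** An as-treated analysis groups patients by what they received. A patient whose study drug is stopped during surgery has usually had the bolus and part of the infusion, and so belongs in that analysis. The rule removes the patient because of a post-randomisation event that lidocaine could itself cause.

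Inclusion then depends on when the complication happened. An arrhythmia in theatre during the infusion takes the patient out. The same arrhythmia in the PACU, with the infusion still running under 3.b, does not.

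Two things are at stake. A safety summary on this set could not show an intraoperative arrhythmia after dosing, whatever the true rate. An efficacy comparison on it would be conditioned on a possible drug effect, so agreement with ITT would reassure less than it appears to.

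**Working it through.** **1. The plan's own figure.** G1 gives 25 per arm, two-sided 0.05, 80% power, d = 0.8, mean 149 mg and SD 37 mg.

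- n per arm = 2 × ((1.960 + 0.842)/0.8)² = 24.5, rounded up to 25. The stated size reproduces by the normal approximation; a t-test calculation gives 26.
- Target difference = 0.8 × 37 = 29.6 mg, and 29.6/149 = 19.9%, which matches the stated 20%.

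The documents give no figure for the as-treated rule. The SD and target difference serve below only as yardsticks.

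**2. Exposure at the time of exclusion.** The bolus comes with induction and the infusion starts before incision (3.b, F2). F3 speaks of study medication being stopped, which implies that it had started. Only a complication before the bolus would leave a patient unexposed.

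**3. Safety.** The documents give no complication rates. Assume k = 1, 2 or 3 of 25 lidocaine patients have an intraoperative arrhythmia after dosing and nobody else in that arm is excluded. Intervals are Clopper-Pearson 95%.

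| k | All exposed | As-treated under the rule |
|---|---|---|
| 1 | 1/25 = 4% (0.1 to 20.4%) | 0/24 (upper limit 14.2%) |
| 2 | 2/25 = 8% (1.0 to 26.0%) | 0/23 (upper limit 14.8%) |
| 3 | 3/25 = 12% (2.5 to 31.2%) | 0/22 (upper limit 15.4%) |

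The zero in the last column follows from the rule and carries no information about the drug.

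**4. Opioid consumption.** Let k lidocaine and m placebo patients be excluded, with mean consumption D mg above the rest of their own arm (the same D in both arms). If the rest of an arm averages r, the full lidocaine mean is r + (k/25)D and the as-treated mean is r. The lidocaine-minus-placebo difference therefore moves by

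shift = -((k - m)/25) × D.

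Negative values favour lidocaine. With m = 0 and D = ±37 mg (1 SD, assumed):

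| k | D = +37 mg | D = 0 | D = -37 mg |
|---|---|---|---|
| 1 | -1.48 mg | 0 | +1.48 mg |
| 2 | -2.96 mg | 0 | +2.96 mg |
| 3 | -4.44 mg | 0 | +4.44 mg |

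With k = m the shift is 0, given the same D in both arms. The largest value is 4.44/29.6 = 15% of the target difference. The standard error of the difference at 25 per arm is 37 × √(2/25) = 10.5 mg, so it is also about 0.4 of a standard error.

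**The case against.** A reader might infer that the rule biases the as-treated analysis towards lidocaine. The documents do not support that for efficacy. The rule covers both arms and every kind of intraoperative complication. The sign of the shift depends on the excluded patients' opioid use and on how exclusions fall between arms, and the plan gives neither.

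A reader might also infer that the arrhythmias feared most vanish from the trial. They do not. Only intraoperative cases leave, and only from this set. F3 and I1 keep them in ITT, F3 records all adverse events for 12 weeks and follows patients whose event came after dosing, and the I1 review of adverse events is not limited to the as-treated set. The plan does not assign safety reporting to that set, so the table in step 3 is one that might be produced, not one that is specified.

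Finally, a supportive analysis that omits early stops is a familiar per-protocol analysis, and a shift of at most 4.4 mg would be hard to tell from noise in 50 patients.

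All of this limits the consequence. It does not rescue the rule. The label says treatment received, while the rule selects on outcome. The rule sits in the two safety sections, and no other safety set is defined, so an analyst could well use this one.

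**Conclusion.** The as-treated rule is wrong as written and should be corrected. It excludes patients who have normally been exposed, on a post-randomisation event that study drug may cause, and keeps patients whose complication came later.

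For safety the direction is certain: any as-treated summary would omit intraoperative arrhythmias after dosing. Its size (0% shown instead of 4 to 12%) rests on assumed counts of 1 to 3. For opioid use the result is selection bias of unknown sign, about -4.4 to +4.4 mg for 1 to 3 lidocaine-only exclusions at ±1 SD, and none if exclusions balance and the excluded patients differ equally in both arms. A claim of bias in favour of lidocaine would go beyond the documents.

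This does not undermine the primary result as long as ITT keeps these patients, as F3 and I1 state. That retention is itself in doubt while another paragraph of F3 excludes such patients from the study.

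**What to change.** In F3 and I1, replace the exclusion with a definition along these lines: *the as-treated set is every patient who received any study drug, bolus or infusion, grouped by the product received, including patients whose study drug was stopped.* State that all safety summaries use this set. If an analysis without early stops is also wanted, call it per-protocol, define it by the administered volume, and label it supportive and open to selection bias. List the sets and the outcomes that use each in G2.

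Two sets of statements must be reconciled at the same time:

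- Retention in ITT (F3, I1) against exclusion from the study (later in F3). For analysis purposes, patients with an event after dosing should stay in ITT and in the safety set. The text should say that their outcomes are still collected after they are withdrawn from study treatment or unblinded.
- The statement in F3 and I1 that the infusion is complete after surgery, against the 24-hour postoperative infusion in E1, 3.b and F2. The reason given for treating postoperative complications differently rests on it.

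The cost is small. D2 already has the total administered volume recorded, and F3 already captures adverse events to 12 weeks. Continued outcome collection for withdrawn patients has to be spelled out. The downside is that the as-treated set will be close to ITT and so will add little as a separate efficacy analysis.
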